## 7 SAFETY ASSESSMENTS

The participants will attend a safety visit on Day 29 ( $\pm 1$  day), Day 36 ( $\pm 2$  days), Day 43 ( $\pm 2$  days) and Day 64 ( $\pm 3$  days) for Follow-Up procedures as shown in the Schedule of Assessments (Section 1.3).

### 7.1 Clinical Laboratory Evaluations

Clinical laboratory evaluations and urine drug screens will include the analytes listed in Table 4. Approximate blood sampling volumes are provided in Section 14.1.

All blood and urine analyses will be conducted on-site or at a central laboratory at the sampling times indicated in the Schedule of Assessments (Section 1.3). The clinical laboratory evaluation results will be collected at Screening in time for results to be reviewed prior to the first study drug administration. For abnormal values, additional testing may be performed, or clinical laboratory evaluations may be added to evaluate the abnormal values. Clinically significant values should be followed until resolution or until they reach a stable state.

**Table 4: Clinical Laboratory Evaluations**

Blood Chemistry Amylase BUN Creatinine Glucose Sodium Potassium Phosphate Chloride Calcium AST ALT GGT Alkaline phosphatase Total, direct, indirect bilirubin Uric acid Albumin Total protein Lactate dehydrogenase	Urinalysis Glucose Bilirubin Ketone Specific Gravity Blood pH Protein Urobilinogen Nitrite Leukocyte Esterase
Hematology Hemoglobin Hematocrit RBC count RBC indices (MCV, MCH, MCHC) Platelet count White blood cell count with differential	Urine drug screen Amphetamines Benzodiazepines Cocaine MDMA Opiates
Other Testing Urine pregnancy test (WOCBP only) Follicle stimulating hormone a	

Abbreviations: ALT = alanine aminotransferase; AST = aspartate aminotransferase; BUN = blood urea nitrogen; GGT = gamma-glutamyl transferase; MCH = mean corpuscular hemoglobin; MCHC = mean corpuscular hemoglobin concentration; MCV = mean corpuscular volume; RBC = red blood cell; WOCBP = women of childbearing potential.

a Suspected perimenopausal female participants only, based on surgical history or <12 months amenorrhea.

### 7.2 12-Lead Electrocardiogram

The 12-lead ECG will be collected within approximately 30 minutes predose and at the end of the dose session. The 12-Lead ECG should be obtained after the participant has rested in the

supine position for at least 5 minutes. The ECG machine used should automatically calculate the HR and PR, QRS, QT and QTcF intervals.

### 7.3 Vital Signs and Temperature

Vital signs, including HR, BP, and temperature will be collected after the participant has rested in the seated position for at least 5 minutes. Predose vital signs should be collected within 10 minutes predose. Blood pressure and HR will be collected 10 minutes predose and at 30-minute intervals ( $\pm 15$  min) post-initial dose-administration until the end of the dose session. In addition, BP and HR will be recorded 15 minutes (+5 minutes) before administration of the booster dose. This pre-booster vital signs collection is the equivalent of the 90-minute vital signs collection timepoint. Temperature will be recorded predose (within 10 minutes) and at 60-minute intervals ( $\pm 15$  min) post-initial dose-administration, until end of the dose session.

### 7.4 Physical Examinations

A physical examination, including body weight (Screening and EOS) and height (Screening only), and assessments of the head, eyes, ears, nose, throat, skin, neurological, lungs, cardiovascular system, abdomen, and lymph nodes will be conducted.

### 7.5 Pregnancy Testing

Dosing should not proceed until a negative pregnancy test is confirmed.

- Refer to [Section 6.1](#) for pregnancy testing entry criteria.
- A urine pregnancy test will be performed at Screening, and Day 1, to confirm eligibility.
- Pregnancy testing (urine) will be conducted prior to dosing on dosing days and on Day 29.
- A positive or inconclusive urine pregnancy test should be confirmed by a serum pregnancy test (see [Section 7.8.3.1](#)).
- Additional serum or urine pregnancy tests may be performed, as determined necessary by the Investigator or required by local regulation, to establish the absence of pregnancy at any time during the participant's participation in the study.
  - The Investigator is responsible for review of medical history, menstrual history and recent sexual activity to decrease the risk for inclusion of a woman with an early undetected pregnancy.

### 7.6 Columbia-Suicide Severity Rating Scale

The C-SSRS will be used to assess suicide potential or tendency as a study entry criterion and monitored throughout the study.

The C-SSRS is a semi-structured interview designed to assess the severity and intensity of suicidal ideation, suicidal behavior and non-suicidal self-injurious behavior over a specified time period. The measurement of suicidal ideation is based on five 'yes' or 'no' questions with accompanying descriptions arranged in order of increasing severity. If the participant answers 'yes' to either questions 1 or 2, the intensity of ideation is assessed in five additional questions related to frequency, duration, controllability, deterrents and reasons for the most severe suicidal ideation. Suicidal behavior is assessed by asking questions categorizing behaviors into actual, aborted and interrupted attempts; preparatory behavior, and non-suicidal self-injurious behavior.

If any item(s) on the C-SSRS are answered ‘yes’, the Investigator must review the participant’s responses in order to (a) at the Screening visit and Baseline/Preparatory session to determine the participant’s study eligibility and potential need for referral to a mental health professional, and (b) during the study evaluate the participant’s need for appropriate medical management such as a referral to a mental health professional, or appropriateness of further study drug administration in consultation with the Medical Monitor and Sponsor.

A significant risk of suicide is defined as a ‘yes’ in answer to:

- (a) questions 4 or 5 on the suicidal ideation section; or,
- (b) any questions on any item in the suicidal behavior section.

This must be reported as an AE or SAE as appropriate and followed up accordingly. Additionally, if a participant responds ‘yes’ to any of the suicidal ideation questions 1 through 3, the Investigator should apply clinical judgement to determine the need for reporting this as an AE or SAE and the need for any appropriate referral.

For any participant who responds ‘yes’ to relevant questions post-study drug administration, they will be handled appropriately.

## **7.7 Adverse Event Reporting**

Adverse events will be elicited through non-leading questions and spontaneous reporting by participants.

At all times, the Investigator should be alert to comments that imply an AE.

The Investigator is responsible for evaluating AEs and for the appropriate medical care of participants during the study.

### **7.7.1 Definition and Criteria**

#### *7.7.1.1 Adverse Event*

An AE is any untoward medical occurrence in a study participant which either emerges, or worsens from enrollment/randomization, during the clinical study, regardless of its potential relationship to the medicinal product. An AE, therefore, can be any unfavorable or unintended sign, including a clinically significant abnormal laboratory finding, symptom, or disease temporally, whether or not it is considered to be study drug-related.

Examples of an AE include:

- Exacerbation of a pre-existing condition including either an increase in frequency and/or severity of the condition.
- New conditions detected or diagnosed.
- Signs or symptoms of a drug interaction.
- Signs or symptoms of a suspected overdose of either IMP or a concurrent medication (overdose per se should not be reported as an AE/SAE).
- A new laboratory abnormality occurring after the start of the study (i.e., following enrollment/randomization) or are present at baseline and significantly worsen following the start of the study that results in discontinuation of the study drug, medical treatment or further follow-up. The Site Investigator will exercise their medical and scientific

judgement in deciding whether an abnormal laboratory finding, or other abnormal assessment is clinically significant.

Note: abnormal laboratory or other values obtained during Screening that preclude a participant from entering the study are not considered AEs but will be recorded as the reason for screen failure.

Adverse events may include pre- or post-treatment events that occur as a result of Protocol-mandated procedures (i.e., invasive procedures, modification of participant's previous therapeutic regimen).

A medical intervention to address an AE is an "action taken" and not an AE itself.

#### 7.7.1.2 *Serious Adverse Event*

An SAE is any untoward medical occurrence that, at any dose:

- Results in death,
- Is life-threatening,

Note: The term 'life-threatening' in the definition of 'serious' refers to an event in which the participant was at risk of death at the time of the event. It does not refer to an event, which hypothetically might have caused death, if it were more severe.

- Requires hospitalization or prolongation of existing hospitalization,

Note: In general, hospitalization signifies that the participant has been detained (usually involving at least an overnight stay) at the hospital or emergency ward for observation and/or treatment that would not have been appropriate in the physician's office or outpatient setting. Complications that occur during hospitalization are AEs. If complication prolongs hospitalization or fulfils any other serious criteria, the event is serious. When in doubt whether 'hospitalization' occurred or was necessary, the AE should be considered serious.

- Results in persistent or significant disability or incapacity,

Note: The term 'disability' means a substantial disruption of a person's ability to conduct normal life functions. This definition is not intended to include experiences of relatively minor medical significance such as uncomplicated headache, nausea, vomiting, diarrhea, influenza and accidental trauma (e.g., sprained ankle) which may interfere or prevent everyday life functions but do not constitute a substantial disruption.

- Is a congenital abnormality or birth defect,
- Is an important medical event.

Note: Medical or scientific judgement should be exercised in deciding whether reporting is appropriate in other situations, such as important medical events that may not be immediately life-threatening, or result in death or hospitalization, but may jeopardize the participant or may require medical or surgical intervention to prevent one of the other outcomes listed in the above definition. These should also be considered serious. Examples of such events are invasive or malignant cancers, intensive treatment in an emergency room or at home for allergic bronchospasm, blood dyscrasias or convulsions that do not result in hospitalization, or development of drug dependency or drug abuse.

Note: The terms "serious" and "severe" ARE NOT synonymous. The term "severe" is often used to describe the intensity (severity) of a specific event (as in mild, moderate or severe myocardial infarction); the event itself, however, may be of relatively minor medical

significance (such as severe headache). This is NOT the same as “serious”, which is based on participant/event outcome or action criteria described above and are usually associated with events that pose a threat to a participant’s life or functioning. A severe AE does not necessarily need to be considered serious. For example, persistent nausea of several hours duration may be considered severe nausea but not an SAE. On the other hand, a stroke resulting in only a minor degree of disability may be considered mild but would be defined as an SAE based on the above criteria. Seriousness (not severity) serves as a guide for defining regulatory reporting obligations.

Only SAEs will be recorded from the time of informed consent until the time of enrollment/randomization.

#### 7.7.1.3 *Adverse Events of Special Interest*

The Sponsor will pay special attention to a subset of AEs; these AEs will be marked in the eCRF with the denotation AESIs whether serious or non-serious. These should be reported to the Sponsor or delegate; they include:

- Grade 3 hypertension, SBP  $\geq 160$  mmHg or DBP  $\geq 100$  mmHg, requiring the need for medical intervention with more than one drug or more intensive therapy than previously used.
- Significant cardiovascular events
- AEs related to suicide risk, such as; suicides, suicide attempts, self-injurious behavior associated with suicidal ideation and suicidal ideation judged to be serious or severe in the opinion of the Investigator.
- Signals of abuse potential AE involving terms of behavioral addiction, drug abuser, substance abuser.

If an AESI is an SAE or if it involves suicide risk, it should be reported to the Sponsor or delegate within 24 hours of the site’s awareness of the event.

### 7.8 **Evaluating Adverse Events and Serious Adverse Events**

Care will be taken not to introduce bias when detecting AEs and/or SAEs. Open-ended and non-leading verbal questioning of the participant is the preferred method to inquire about AE occurrences.

All AEs will be assessed on two descriptive parameters: severity and relationship to the study drug:

- Severity refers to the severity of an event and references impact on a participant’s functioning.
- Relationship refers to the likelihood that the event being assessed was caused by the study drug.

The Investigator will make an assessment of severity for each AE and SAE reported during the study. Adverse events will be assessed according to the general guidelines for grading:

- **Mild:** Usually transient and may require only minimal treatment or therapeutic intervention. The event does not generally interfere with usual activities of daily living

- **Moderate:** Usually alleviated with additional specific therapeutic intervention. The event interferes with usual activities of daily living, causing discomfort but poses no significant or permanent risk of harm to the subject
- **Severe:** Interrupts usual activities of daily living, or significantly affects clinical status, or may require intensive therapeutic intervention

For AEs and SAEs, the relationship to the study treatment is to be assessed according to the following definitions:

- **Not related:** There is no reasonable association between the study treatment and the suspected event.
- **Unlikely related:** It is doubtful that there is an association between the study treatment and the suspected event. The event could have been produced by the participant's clinical state or other modes of therapy administered to the participant.
- **Possibly related:** The suspected AE may or may not follow a reasonable temporal sequence from study drug administration. The event could have been produced or mimicked by the participant's clinical state or by other modes of therapy concomitantly administered to the participant.
- **Probably related:** The suspected AE follows a reasonable temporal sequence from study treatment administration, abates upon discontinuation of the treatment; and cannot be reasonably explained by the known characteristics of the participant's clinical state.

When assessing the relationship to the study drug, the following criteria will be considered:

- Known class effect
- Positive rechallenge
- Positive dechallenge (resolution after a dose session, in absence of other interventional treatment)
- Biological plausibility
- Lack of alternative explanation – concomitant drug or disease

## 7.8.1 Reporting Procedures and Requirements

### 7.8.1.1 Time Period and Frequency for Collecting AE and SAE Information

All SAEs will be collected from the signing of the informed consent form (ICF) until the EOS visit at the timepoints specified in the Schedule of Assessments (see [Section 1.3](#)).

All AEs will be collected from enrollment/randomization until the EOS visit at all interactions with the participants (see [Section 1.3](#)). A baseline safety assessment will occur after Screening. Medical occurrences that begin before the start of study intervention but after obtaining informed consent will be recorded as medical history/current medical conditions, not as AEs.

The Investigator is not obligated to actively seek information on AEs or SAEs after conclusion of the study participation. However, if the Investigator learns of any SAE, including a death, at any time after a participant has been discharged from the study, and the Investigator considers the event to be reasonably related to the study intervention or study participation, the Investigator must promptly notify the Sponsor.

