Study Visit	Visit Timing	Brief Description of Events
Dose Session 1 (Visit 3 – Within 4 days of Baseline/ Preparatory Session	Day 1 – Predose	
Prior to enrollment (Part A) or randomization (Part B), an eligibility criteria review, a negative urine pregnancy test (WOCBP only), and urine drug screen will be required. Once confirmed that the participant meets all criteria, they will be enrolled (Part A) or randomized (Part B) onto the study. Predose assessments will then be performed (including vital signs, temperature, 12-lead ECGs, and C-SSRS).
 
Participants should have fasted (water only) for at least 2 hours prior to dosing and for at least 2 hours after the booster dose.
 
(Methyl) xanthine- and caffeine-containing products should be avoided for 2 hours predose until at least 8 hours after the initial dose.

	Day 1 – Dose Session 1 (~8 hours)	
Recording begins immediately prior to dosing.
 
Following dosing, adverse event monitoring begins.
 
The open-label treatment for Part A is:
 
 
Methylone 150 mg, with a booster administration of 100 mg administered 90 (±10) minutes later.
 
 
The two blinded study treatment arms for Part B are:
 
 
Methylone 150 mg, with a booster administration of 100 mg administered 90 (±10) minutes later.
 
Matched placebo (initial and booster).
 
 
Safety will be assessed at the following timepoints during the dose session:
 
 
BP and HR will be recorded 10 minutes predose and at 30-minute intervals (±15 minutes) post-administration until the end of the dose session 
 
In addition, BP and HR will be recorded within 15 minutes (+5 minutes) prior to administration of the booster dose (equivalent of 90-minute timepoint)
 
 
 
Temperature will be recorded predose and at 60-minute intervals (±15 minutes) post-initial dose-administration, until end of the dose session
 
12-lead ECG will be performed predose and at the end of the dosing session
 

	Day 1 – Discharge	
Prior to discharge, the dosing session monitor will encourage the participant to reflect on their experience.

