### 8.4.1 Adverse Events

Treatment-emergent AEs (TEAE) are defined as any AE with an onset date on or after the date of first administration of study treatment and not more than 7 days after the last dose unless otherwise suspected to be related to study drug. For AEs with missing or partial start dates, if there is no clear evidence that the AEs started before or after study treatment, the AEs will be classified as TEAEs. Suspected to be drug related TEAEs include Relationship to study drug: “Possibly Related”, “Probably Related”.

An overall summary of the number and percentage of subjects with below will be presented:

- Any TEAEs
- serious TEAEs
- TEAEs related to study drug
- serious TEAEs related to study drug
- TEAEs leading to study discontinuation
- TEAEs leading to drug withdrawn
- TEAEs leading to death
- TEAEs of special interest.

Also, the TEAEs will be presented by System Organ Class (SOC), and PT. Subjects will be counted only once for each SOC and PT.

In addition, subjects with TEAEs in various severity categories will be presented based on the maximum severity of a specific TEAE for a subject. Similarly, subjects with TEAEs in various relationship categories will be presented based on the most related relationship (from ‘not related’, ‘unlikely related’, ‘possibly related’, to ‘probably related’) of a specific TEAE for a subject.

All AEs will be presented in individual by-subject data listings. Listings of any subject experiencing TEAEs related to study drug, AESI and an SAE will be provided separately.

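### Non-serious events arising on Day 1 between randomization and first dose are AEs under some protocol rules and medical history under another, and the SAP's date-only rule would count them as treatment-emergent

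*Protocol*

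**What the plan says.** **AEs start at randomization.** Protocol 7.7.1.1 defines an AE as something that "either emerges, or worsens from enrollment/randomization, during the clinical study", and SAP 6.2.1.1 repeats that definition. Protocol 7.8.1.1 states: "All AEs will be collected from enrollment/randomization until the EOS visit at all interactions with the participants". Protocol 7.8.1.2 gives the same recording period. The end of 7.7.1.2 agrees by implication: "Only SAEs will be recorded from the time of informed consent until the time of enrollment/randomization".

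**AEs start at dosing.** Later in the same paragraph of 7.8.1.1, anything that arises after consent but before study intervention "will be recorded as medical history/current medical conditions, not as AEs". In the Dose Session 1 row of 4.2: "Following dosing, adverse event monitoring begins".

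**Order of events on Day 1.** Section 4.2 places randomization after the eligibility checks. The predose vital signs, temperature, ECG and C-SSRS come next, and then the dose.

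**C-SSRS.** Protocol 7.6 requires a positive answer to ideation item 4 or 5, or to any behavior item, to be reported as an AE or SAE. It states no exception for predose assessments.

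**Treatment emergence.** SAP 8.4.1 defines a TEAE as "any AE with an onset date on or after the date of first administration of study treatment", with an upper limit of 7 days after the last dose unless the event is suspected to be drug-related. It uses no clock time.

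**The concern.** Two protocol rules, in one paragraph, classify the same event in opposite ways, and no passage says which prevails. The disputed window is short, but every randomized participant who is dosed passes through it while being actively assessed. A site following 7.7.1.1 and 7.8.1.2 would use the AE page. A site following the medical-history sentence would not.

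It would be natural to dismiss this on the ground that predose events are not treatment-emergent anyway. The SAP does not say that. Randomization and first dose fall on the same calendar date, so a date comparison cannot separate a predose event from a postdose one. An event entered as an AE would be reported as treatment-emergent although no drug had been given. TEAE incidence and severity is a named secondary endpoint for Part B (Protocol Table 2).

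**Working it through.** The plan states no figure on this point, so there is none to reproduce. The check applies each rule to four onset windows for a non-serious event, assuming first dose on the day of randomization.

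| Onset | Randomization rule (7.7.1.1, 7.8.1.1, 7.8.1.2) | Medical-history sentence (7.8.1.1) | SAP 8.4.1 date test, if entered as an AE | Test against time of first dose |
|---|---|---|---|---|
| After Baseline, before Day 1 | not an AE | medical history | not a TEAE | not a TEAE |
| Day 1, before randomization | not an AE | medical history | TEAE | not a TEAE |
| Day 1, after randomization, predose | **AE** | **medical history** | **TEAE** | **not a TEAE** |
| Day 1, postdose | AE | not applicable | TEAE | TEAE |

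Only the third row puts the two protocol rules in conflict. In the second row both keep the event off the AE page, so the SAP test should not meet it. Section 7.8.1.2 adds a further reference point, a baseline safety assessment, whose timing is given only as after Screening.

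**C-SSRS case.** A predose positive answer of the kind named in 7.6, judged non-serious, must be reported as an AE under 7.6. If what it describes began before study intervention, 7.8.1.1 sends it to medical history. It reaches the TEAE table only if the participant is then dosed on that date. A participant who is never dosed is outside the Safety population.

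**The SAP's own practice elsewhere.** SAP 8.4.3 and 8.4.4 take the measurement before the initial dose as the session baseline for vital signs and ECG. SAP 6.2.6 and 8.4.6 count C-SSRS ideation and behavior only from first administration. So a new predose ECG abnormality entered as an AE would be session baseline under 8.4.4 and treatment-emergent under 8.4.1. A predose C-SSRS finding would be left out of the C-SSRS summary but could enter the TEAE table.

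**Scale.** Planned size is 64, or 32 per arm (Protocol 9.2).
- One reclassified participant: 1/32 = 3.1 percentage points in that arm for a preferred term.
- Up to 25 sites: 64/25 = about 2.6 participants per site.
- Let b be the proportion in each arm with a predose event counted as a TEAE, independent of other events, and q the true any-TEAE proportion. The reported proportion is q + b(1 − q). The arm difference becomes (q_A − q_P)(1 − b). Counts rise in both arms and the difference shrinks by the factor 1 − b.

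Neither document gives a value for b.

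**The case against.** **The window is hours long and safety is descriptive.** This stands. SAP 8.4 plans no formal safety testing, and a predose event cannot depend on the blinded drug. A known predose event ought also to stay out of the related-TEAE tables. It is why the point is modest.

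**The date rule is a deliberate, cautious convention.** This stands in part. SAP 8.4.1 counts events of unclear timing as TEAEs, and SAP 7.2.1 sets a fully missing onset date to the first dose. That protects against undercounting when timing is unknown. It gives no reason to count an event known to precede the dose.

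**The wording in 4.2 may only describe in-session monitoring.** This is a fair reading, but it leaves the conflict inside 7.8.1.1.

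**Many predose findings are outside the dispute.** This stands. An abnormality first seen at the predose ECG is not thereby shown to have begun after randomization. Something already present and unchanged is not an AE under the randomization rule.

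A reader might infer more than the documents support:
- *Harms from washout or the Preparatory Session go unrecorded.* Non-serious events before randomization are recorded as medical history, listed (Protocol 10.1) and summarized by preferred term (SAP 8.2.3.3). The fix below leaves them there.
- *SAE collection is contradicted.* Protocol 7.7.1.2, the opening of 7.8.1.1, and 7.8.1.3 all collect SAEs from consent. The medical-history sentence should say that it does not override this, but the intent is clear.
- *AESI counts are materially affected.* Nothing points to predose AESIs. The hypertension AESI, for example, requires intervention with more than one drug or more intensive therapy than before.
- *Sites will diverge, or a given number of participants will be misclassified.* Divergence is a risk, not shown to occur, and any count would rest on an event rate that neither document supplies.

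**Conclusion.** The inconsistency is real and unreconciled for non-serious events that begin or worsen on Day 1 after randomization and before the first dose. The SAP's date-only test adds to it by labelling such an event treatment-emergent whenever it is entered as an AE and the participant is dosed that day. The expected effect is a small, non-differential inflation of descriptive TEAE counts, with possible inconsistency between sites. One participant is 3.1 percentage points in an arm of 32. No bias between arms is expected, although a chance imbalance is possible at this size. Efficacy and power are untouched. The conclusion rests on the order of Day 1 procedures in 4.2 and on first dose falling on the randomization date. The eCRF is not among the documents, so whether it already captures onset time is unknown.

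**What to change.** 1. **Protocol 4.2, 7.7.1.1, 7.8.1.1 and 7.8.1.2:** state one AE start point. Randomization is the natural choice because most passages already use it. Say when the baseline safety assessment in 7.8.1.2 takes place.
2. **Protocol 7.8.1.1:** limit the medical-history sentence to non-serious events before that point. State that it does not override SAE collection from consent or the C-SSRS reporting rule in 7.6.
3. **SAP 8.4.1:** for Day 1 events, define a TEAE by onset relative to the first administration, using an onset time or a before/after-first-dose flag. List known predose Day 1 AEs as not treatment-emergent. Keep counting events of unknown timing as TEAEs.

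The cost is wording in both documents and, unless the eCRF already collects it, one onset-time field or flag for Day 1 AEs. No new assessment, visit or change in sample size is needed.
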